5.2 Treatment assignment

We designed a two-stage randomization process to study both direct treatment and spillover effects of health insurance.

In a first stage, we randomly assigned villages to one of five village-level arms. A village-level arm is defined by the percentage of households within the village assigned to each of the four household-level study arms defined in subsection 4.2.1. The percentage allocations to the 4 household-level arms are given in the last 4 columns of Table 1. The percent of villages assigned to each of the 5 village-level arms are in the second column. Villages were matched before this first stage randomization.⁷

Table 1: IHIE Two-Stage Randomization Design

Village-level arms (%)		Household-level arms (%)			
Arm	Village allocation	Group A	Group B	Group C	Group D
I	15	30	50	10	10
II	15	30	10	50	10
III	15	30	10	10	50
IV	35	70	10	10	10
V	20	10	30	30	30
Total	100	40	20	20	20

In a second stage, we randomly assigned households within a village to the four arms according to the allocation probabilities assigned to the village. Households were matched before this second stage randomization.⁸

The target enrollment for each of the 4 household-level arms, unconditional on village-level arm, was 4,500 households for condition A and 2,250 households for each of conditions B, C and D. Due to some attrition between listing and completion of baseline, our final randomized sample amounted to 11,089 households in 424 villages in the two districts.

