5.3 Data Collection

We conducted 6 rounds of data gathering: (1) a listing exercise; (2) a baseline survey; (3) an enrollment survey; (4) a 12 month follow-up survey, which uses a novel design we call a Post-Health Event Survey

⁷Specifically, we first stratified villages into quintiles of: # eligible hhds per village. Within each quintile, we created blocks of 20 villages. Using data from our listing exercise on average values for certain variables (among eligible hhds in a village), create blocks as follows:

- Mahalanobis matching on: education, age of household head, # children, # rooms in house
- Caliper matching on binary variables: major illness, unemployment in household

Within a village block, we randomly assign villages to 5 village-level conditions (without replacement).

⁸Specifically, within each village, we first created blocks of 10 eligible and consented households. Using household-level data from listing survey, create blocks as follows:

- Mahalanobis matching on: education, age of household head, # children, # rooms
- Caliper matching on binary variables: major illness, unemployment in household

Within each block of households, we randomly allocate households to the 4 household-level conditions in accordance with the village-level assignment probability condition (without replacement).

(PHES); (5) an 18 month follow-up survey, which we label a midline survey; and (6) a 4 year follow-up survey, which we call an endline.

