In addition, we will estimate two substantively different specifications to abstract away from methods of access to insurance and towards the mere fact of access to insurance. On one, we replace the four household group indicators with an indicator for whether the household was in group A, B or C and we replace the four village-level arm share variables with the share in groups A, B or C.¹¹ Additionally, we will estimate a specification where σ_j^v is replaced by the total share of the village eligible for RSBY, including both the share assigned to A, B and C as well as the share of the village with BPL cards or in certain eligible occupational classifications (who were therefore RSBY eligible).

Control variables. We first estimate a variant of the regression model above without any controls X_{ijs} , where s indicates a time that may not be equal to t . We then estimate a specification where X_{ijs} is a vector of baseline controls (i.e., X_{ijs} at time $s = 0$). We will use machine learning methods to select these control variables. Finally, we will run specifications where X_{ijs} may include so-called “coloring variables” that shed light on mechanisms of impact, welfare effects, and the dosage of treatment. In the latter case, we will include interactions of treatment variables with coloring variables, the same manner in which we estimate heterogeneous treatment effects. These coloring variables are listed in section 8.

Weighting. This regression can be weighted in multiple ways. We could either weight each household equally or weight each village arm identically. When examining household-level access We choose to weight each household equally because no household is obviously more informative than any other, especially when examining questions about the impact of insurance on households. When examining spillovers, we will weight villages equally.

Standard errors. We use the cluster robust HC2 standard errors at the village level. [name], Jiang, and [name] (2019) shows that this is a conservative variance in two-stage randomized experiments.

Spillovers. To address the possibility of spillovers from, e.g., giving some households access to insurance in one way affects households not given access to insurance in that way, we do a few things.

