7.2 Complier average treatment effect (CATE)

Our second parameter of interest is the CATE estimate for the impact from uptake of insurance. Our basic regression model to estimate this has a two-stage least squares structure:

$$y_{ijt} = \alpha + \theta s_j + \phi z_{ij} + \rho s_j z_{ij} + \psi X_{ij} + u_{ijt} \quad (3)$$

where z_{ij} is the binary enrollment variable by household i in village j , and $s_j = \sum_{i=1}^{n_j} z_{ij}/n_j$ is the enrollment rate in village j . We estimate this equation using instrumental variables, d_j^v , d_{ij}^h , and $d_j^v d_{ij}^h$ (see Appendix E.2 of [name], Jiang, and [name] (2019), for $(s_j, z_{ij}, s_j z_{ij})$). The remaining variables are defined as in equation (2). In particular, the control variables and weighting are managed as they are in the previous section.

Identification. The exclusion restriction for CATE estimation is that treatment assignment only affects household outcomes through the decision to enroll in RSBY (see [name], Jiang, and [name] (2019) for details). Note we are not instrumenting *utilization* of RSBY, which would require a stronger exclusion restriction. We are instrumenting enrollment in RSBY.

Spillovers. To address the possibility of spillovers, we do many of the things we do for the ITT analysis. For example, as discussed by [name], Jiang, and [name] (2019), we will use the cluster robust HC2 variance or the weighted average of individual and cluster robust HC2 variances. The most important difference is the assumptions required for unbiased estimation with spillovers, as given in [name], Jiang, and [name] (2019). Beyond partial non-interference as before, we must assume that for noncompliers their treatment assignment does not affect their outcome through the enrollment of other units. Moreover, we test for the existence of spillovers by testing the null hypothesis that $\theta = 0$ and $\rho = 0$.

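### Villages were randomised within matched blocks, but the models and village-clustered standard errors omit the blocks, so between-village (spillover) contrasts are reported less precisely than the design allows

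*Combined protocol and SAP*

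**What the plan says.** Both stages of randomisation were blocked. On the first, Section 5.2 states that "Villages were matched before this first stage randomization". Footnote 7 gives the detail: villages were split into quintiles by number of eligible households, then "Within each quintile, we created blocks of 20 villages", matched on listing-survey averages, and the five village-level arms were drawn without replacement inside each block. On the second, footnote 8 says that "within each village, we first created blocks of 10 eligible and consented households". The result was that "our final randomized sample amounted to 11,089 households in 424 villages in the two districts".

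The analysis sections do not return to these blocks. Equations (1) to (4) contain village-arm terms, household-arm terms, their interactions and a covariate vector, but no block or quintile indicator. For the ITT, Section 7.1 says "We use the cluster robust HC2 standard errors at the village level" and adds that the cited methods paper "shows that this is a conservative variance in two-stage randomized experiments". For the CATE, Section 7.2 says "we will use the cluster robust HC2 variance or the weighted average of individual and cluster robust HC2 variances". The first specification has no controls. The second uses baseline controls chosen by machine learning, with no commitment to the blocks or the matching variables. The word stratum in Section 11.1 refers to the village-level arm, not to a matching block.

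**The concern.** When arms are balanced inside blocks by design, differences between blocks cannot contribute to the difference between arms. A variance computed as if villages had been assigned without blocks still counts those differences as noise. The point estimate keeps the benefit of the blocking, but the interval and the test do not show it.

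This affects quantities identified by comparing villages in different arms. Spillovers are evaluation question 3, they are the stated reason for the two-stage design, and they have Section 11 to themselves. They rest on 424 villages, weighted equally. A spillover test that does not reject is likely to be read as evidence that spillovers are small, so avoidable loss of power in that test matters.

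**Working it through.** **The plan's own figures.** Table 1's totals reproduce. For group A, 0.15×30×3 + 0.35×70 + 0.20×10 = 13.5 + 24.5 + 2 = 40%. A full block of 20 villages splits 3/3/3/7/4 across arms I to V. The only power statement (Section 5.1: a 25% change in hospitalization rate, 10% attrition) concerns study arms and omits alpha, power, base rate and ICC. There is no precision figure for spillovers to reproduce.

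**Inputs from the documents.**
- Households per village: 11,089/424 = 26.15.
- Group D households per village: 2.6 where D is 10% (such as arm IV), 7.8 where D is 30% (arm V).
- Village blocks: 424/20 = 21.2. A quintile holds about 424/5 = 84.8 villages, that is, four full blocks and a remainder, so between 21 and 25 blocks in all.

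**Assumed inputs.** ICC 0.01 to 0.20; R, the share of between-village outcome variance that blocks explain, 0.1 to 0.5.

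**Formula.** A village mean over n households has variance proportional to ICC + (1 − ICC)/n. Blocks can remove only the fraction R of the first part. With share = ICC / [ICC + (1 − ICC)/n], the proportional excess of the block-blind standard error is 1/√(1 − R × share) − 1.

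**All-household contrast, ICC 0.05.** Share = 0.05 / (0.05 + 0.95/26.15) = 0.579. At R = 0.3: 1/√(1 − 0.174) − 1 = 10.0%.

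| Contrast | ICC | Share | R=0.1 | R=0.2 | R=0.3 | R=0.5 |
|---|---|---|---|---|---|---|
| All households (n = 26.15) | 0.01 | 0.209 | 1.1% | 2.2% | 3.3% | 5.7% |
| All households | 0.05 | 0.579 | 3.0% | 6.3% | 10.0% | 18.6% |
| All households | 0.20 | 0.867 | 4.6% | 10.0% | 16.3% | 32.9% |
| Group D, n = 2.6 | 0.05 | 0.121 | 0.6% | 1.2% | 1.9% | 3.2% |
| Group D, n = 7.8 | 0.05 | 0.292 | 1.5% | 3.1% | 4.7% | 8.2% |

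Beta in equation (1) is a group-D contrast because D is the reference arm. Arm III, with half its households in D (n = 13.1, share 0.408), gives 2.1% to 12.1% by the same formula, so a contrast that includes it can go somewhat above 8%.

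**Simulation.** 21 blocks of 20 villages, three household blocks of 10 per village, 400 runs per setting, arm IV against arm V at ICC 0.05.
- All households, R 0.3: true SD 0.0425; mean SE 0.0451 without blocks and 0.0420 with them (7.4% excess); coverage without blocks 96.5%.
- All households, R 0.5, with household blocks explaining 30% of within-village variance: 0.0560 against 0.0516 (8.5% excess), true SD 0.0486, coverage without blocks 98.0%.
- Group D only: 0.0675 against 0.0658 (2.6%) and 0.0715 against 0.0683 (4.7%) in the same two settings.

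The simulated all-household excess is below the tabled 10% and 19% because the simulated household-block effects add variance to village means that village blocks do not explain. In the second setting the within-village part is 0.95×0.3/3 + 0.95×0.7/30 = 0.117, so share = 0.05/0.167 = 0.30, and the formula gives 8.4%. The Monte Carlo error of a coverage figure is about 1 point (√(0.95×0.05/400) = 0.011).

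**Power.** Take a single all-household contrast with 80% power under the block-aware standard error. With an excess of 7.4%, (1.96 + 0.84)/1.074 − 1.96 = 0.65, which is about 74% power. With 10%, it is about 72%.

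**What does not move.** The simulated A−D household contrast had the same standard error with no blocks, village blocks or household blocks (0.0249 at R 0.3, 0.0220 at R 0.5). A second simulation, of the saturated equation (1) with 30 households per village and block effects on village intercepts, changed the lambda standard errors by less than 0.1%. Lambda compares within-village contrasts across village arms, so the village intercept, where the block effect sits, cancels. In that simulation the beta contrast of arms IV and V had an excess of about 4% at R 0.3 and 6% at R 0.5 (ICC 0.05), and 19% at ICC 0.20 and R 0.5.

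**The case against.** The strongest reply is that nothing is invalid and the plan admits the direction: it calls its ITT variance conservative. That stands. The loss is of precision only, and the direct comparisons of household arms, which the power statement concerns, are untouched.

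A second reply is that R may be small. Matching used village averages from the 2013 listing and endline outcomes date from 2019; nothing in the documents shows that blocks still explain 30 to 50% of between-village variance. That also stands, and it is why the size is given only as a range.

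A third is that the machine-learning controls may recover the loss. They may recover part of it in the second specification, but the plan does not require the blocks or matching variables to be selected, and the first specification has no controls.

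A reader might infer more than this supports:
- *That standard errors are 5/12/20/41% too wide at R = 0.1/0.2/0.3/0.5.* This comes from 1/√(1 − R) − 1, which treats a village mean as free of sampling error. With about 26 households per village it is not.
- *That lambda and the whole spillover test suffer.* In equation (1) the Wald null has 4 beta and 12 lambda restrictions, and only the 4 can gain. The drop from 80% to 74% applies to one contrast, not to the joint test.
- *That household blocks should be modelled too.* They lie inside villages, so village clustering already reflects them. Their indicators would also absorb every village-level term, including beta.

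**Conclusion.** The omission is real and worth correcting. Block-blind standard errors are too wide for beta, for all-household penetration effects and, by the same argument although it was not simulated, for the CATE term in the village enrollment rate. The likely excess is modest for group-D-baseline contrasts and can be material for all-household ones, up to about a third at the extreme of the assumed range (ICC 0.20, R 0.5).

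Three assumptions carry this. ICC and R are not in the documents. Block effects are taken to act on village levels, not on treatment effects. And, since 424 is not a multiple of 20, remainder villages are taken to have been randomised in the Table 1 proportions, which the documents do not say; with complete blocks the point estimates are the same with or without block indicators.

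**What to change.** Add village-block indicators, nested in size quintile, to equations (1) to (4), including the no-controls specification, and compute the village-clustered HC2 variance and the spillover Wald tests from that model. One block must be the reference, because equation (1) already carries all five village-arm indicators. State how the remainder villages were randomised and code them accordingly. Do not add household-block indicators. For the CATE, include the same indicators in both stages and say which of the two named variances is primary.

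The cost is a change of wording and roughly 21 to 25 degrees of freedom out of 424 villages. No new data are needed, because the block assignments were created for the randomisation. Fixing this in advance also removes a later choice between block-aware and block-blind results.

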5.4 Treatment Delivery

The population that is eligible for this study would not be eligible for RSBY under the program's usual rules. To make this study possible, we exchanged letters of cooperation with the state in which we conducted the study (Karnataka), the central government agency (Ministry of Labor) responsible for administration of RSBY, and the development organization (GIZ) providing technical support for RSBY.

Sample households were randomized in August 2014 using data from the listing exercise. They were informed of their treatment assignment and, depending on which arm to which they are assigned, given access to insurance or cash in May and June 2015. This step took place roughly 18 months after the baseline due to government constraints. Due to challenges associated with evaluating a government program, we were only able to enroll sample households when the government held its RSBY enrollment drive in early 2015.

We enrolled study households much in the same way the government enrolled RSBY (non-study) eligible households into the program: via a mobile enrollment truck that visited each village. One difference is that we went to each household to ask them if they would like to enroll and took them to the enrollment truck, which was parked in one place in the village. By contrast, the government informed non-study households by delivering paper notices (chits) to each home about when and where the enrollment truck would be in the village.

Roughly 78.4%, 70.4% and 58.6% of households in arms A, B, and C, respectively enrolled in RSBY. Enrollment rates are somewhat higher in Gulbarga than Mysore: 77.9/76.4/64.1% v. 78.8/63.5/52.3% in A/B/C. No one in arm D enrolled.

For all study households that take up insurance, we paid the government their premiums. For households in arms A, this was funded by grant funds. For those in B and C that purchase insurance, this was funded by the respondents' money.

The Karnataka government renewed RSBY automatically for non-study and study households in 2016 and 2017 without any action—even payment—by enrollees. RSBY ended in the state on August 31, 2018, to make way for the new NHPS scheme, which is scheduled to start in late 2018 or early 2019. As of this writing, Karnataka had agreed to roll out NHPS but had not begun the roll-out.

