7.1 Intent-to-Treat (ITT)

Our first parameter of interest is the ITT estimate of the impact of different forms of access to insurance (free, at cost, etc.). Our basic regression model to estimate this is:

$$y_{ijt} = \sum_{v=1}^5 \beta_v d_j^v + \sum_{h=1}^3 \gamma_h d_{ij}^h + \sum_{h=1}^3 \sum_{v=1}^5 \lambda_{hv} d_j^v d_{ij}^h + \delta X_{ijs} + e_{ijt} \quad (1)$$

where y_{ijt} is the outcome for household i in village j at time t ; d_j^v is the indicator for village group $v \in \{1, 2, 3, 4\}$, corresponding to I, II, III, IV and V village groups; d_{ij}^h is the indicator for household

group $h \in \{1, 2, 3, 4\}$; γ_h for $h \in \{1, 2, 3\}$ are ITT estimators for adding one household to groups A, B, and C (D is the baseline); and (β_v, λ_{hv}) measures spillovers.

Coding treatment variables. In order to facilitate interpretation of village group, we estimate an isomorphic specification that recodes the village groups variables, $(d_j^{v=1}, \dots, d_j^{v=5})$, to reflect share of village sample in arms A, B, C, and D, $(\sigma_j^1, \dots, \sigma_j^4)$. The mapping from village group indicators to arm shares is given by the last four columns of Table 1. So, for example, the indicator for village group 1, $d_j^{v=1}$, maps to $(\sigma_j^1, \sigma_j^2, \sigma_j^3, \sigma_j^4) = (0.3, 0.5, 0.1, 0.1)$. Our modified regression model is now:

$$y_{ijt} = \sum_{h=1}^4 \beta_h \sigma_j^h + \sum_{h=1}^3 \gamma_h d_{ij}^h + \sum_{h=1}^3 \sum_{h'=1}^4 \lambda_{hh'} \sigma_j^{h'} d_{ij}^h + \delta X_{ijs} + e_{ijt} \quad (2)$$

where σ_j^h is the proportion of group $h \in \{1, 2, 3\}$ or $\{A, B, C\}$ in village j . Unlike the nonparametric approach given in equation (2), this equation is based on a parametric assumption. However, this specification increases power as it has fewer parameters to be estimated and allows for extrapolation regarding the effects of varying treatment proportions (see Appendix E.1 of [name], Jiang, and [name] (2019)).¹⁰

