First, we measure ITT effects accounting for spillovers at the village level by examining the predicted effects on outcomes for a household in a given group at different shares of the village sample in that group. The specific shares selected could be in-sample shares or out-of-sample shares. We will highlight when we make out-of-sample predictions.¹² In cases where we want to report ITT under sample average spillovers, we will exclude interaction between household arms and, e.g., village arms.

Second, we make assumptions required for unbiased estimation of, (γ_h, λ_{hv}) with spillovers as given in [name], Jiang, and [name] (2019). The key assumption is partial non-interference, i.e., assignments in villages $j' \neq j$ do not influence outcomes in another village j .

Third, to test for the existence of spillover effects, we conduct the Wald test with the null hypothesis that $\beta_v = \beta_{v'}$ and $\lambda_{vh} = \lambda_{v'h}$ for any $v \neq v'$ and $h = 1, 2, 3, 4$. This test can be conducted for both take-up and any outcome variable of interest.

¹⁰<https://imai.fas.harvard.edu/research/files/spillover.pdf>.

¹¹Berry et al. (2018) consider different subsidies and associated extrapolation issues.

¹²Although our study varies the fraction of subjects in a village who receive access to insurance in some form, we do not – as Table 1 shows – give some treatment to no households or some treatment to all households. Therefore, to estimate the above parameter of interest we have to make out-of-sample predictions.

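### Own-share spillover predictions in section 7.1 are undefined in the four-share model until the displaced arm is named, and equation (2) as printed makes this worse

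*Combined protocol and SAP*

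**What the plan says.** Section 5.2 randomises villages to five arms: "The percentage allocations to the 4 household-level arms are given in the last 4 columns of Table 1". Section 7.1 then recodes the village-arm indicators "to reflect share of village sample in arms A, B, C, and D" and enters all four shares in equation (2), with household-group indicators, their interactions with all four shares, and no intercept. The sentence below the equation defines the shares for A, B and C only. Equation (4) in section 7.3 uses three shares and an intercept.

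Under Spillovers, section 7.1 gives as its first approach "examining the predicted effects on outcomes for a household in a given group at different shares of the village sample in that group". It adds: "The specific shares selected could be in-sample shares or out-of-sample shares". Nothing is said about the other three shares. On uptake, section 5.4 reports: "Roughly 78.4%, 70.4% and 58.6% of households in arms A, B, and C, respectively enrolled in RSBY". It also reports that nobody in arm D enrolled.

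**The concern.** A share in a four-part composition cannot move alone. The effect of a larger B share is a different quantity according to whether the extra B households replace D, C or A households. Choosing an in-sample share does not settle it: a B share of 10% occurs in village arms II, III and IV, and a C share of 10% in arms I, III and IV.

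The printed form of equation (2) adds a second problem. Without an intercept, the share coefficients carry the outcome level. An analyst who changes one share and leaves the others predicts for a village whose shares do not sum to 1, and the result can look like a spillover where there is none.

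At stake is whether two analysts following the plan would report the same quantity, and whether the result can be read as a response to wider insurance coverage.

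**Working it through.** **Inputs.** Table 1 (section 5.2), including the rows "II 15 30 10 50 10", "III 15 30 10 10 50" and "IV 35 70 10 10 10" (village arm, % of villages, then A, B, C, D). Arm I is 15% of villages with 30/50/10/10; arm V is 20% with 10/30/30/30. Enrolment rates (section 5.4): A 78.4%, B 70.4%, C 58.6%, D 0%.

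**Step 1: reproduce the plan's figure.** The Total row is the village-weighted sum of the five rows.
- A: 0.15×30 + 0.15×30 + 0.15×30 + 0.35×70 + 0.20×10 = 40
- B: 0.15×50 + 0.15×10 + 0.15×10 + 0.35×10 + 0.20×30 = 20

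C and D also give 20. The printed 40/20/20/20 is reproduced, and each row sums to 100%.

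**Step 2: implied enrolment by village arm.** Formula: 0.784×A + 0.704×B + 0.586×C, with shares in %. This assumes that take-up within an arm is the same in every village arm; the plan gives only pooled and district rates.
- I: 23.52 + 35.20 + 5.86 = 64.6%
- II: 23.52 + 7.04 + 29.30 = 59.9%
- III: 23.52 + 7.04 + 5.86 = 36.4%
- IV: 54.88 + 7.04 + 5.86 = 67.8%
- V: 7.84 + 21.12 + 17.58 = 46.5%

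**Step 3: move one share by 40 points.** Each entry is the difference between two randomised village arms that differ in exactly two shares.

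| Share raised | D displaced | C displaced | B displaced | A displaced |
|---|---|---|---|---|
| B, 10% to 50% | +28.2 (III to I) | +4.7 (II to I) | – | -3.2 (IV to I) |
| C, 10% to 50% | +23.4 (III to II) | – | -4.7 (I to II) | -7.9 (IV to II) |
| A, 30% to 70% | +31.4 (III to IV) | +7.9 (II to IV) | +3.2 (I to IV) | – |

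The sign depends on the displaced arm for B and C. For A it is always positive.

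**Step 4: district rates (section 5.4).** Gulbarga is 77.9/76.4/64.1% and Mysore 78.8/63.5/52.3% for A/B/C.
- B displacing A: 0.4×(76.4 - 77.9) = -0.6 in Gulbarga; 0.4×(63.5 - 78.8) = -6.1 in Mysore
- C displacing A: 0.4×(64.1 - 77.9) = -5.5; 0.4×(52.3 - 78.8) = -10.6
- C displacing B: 0.4×(64.1 - 76.4) = -4.9; 0.4×(52.3 - 63.5) = -4.5

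The signs hold in both districts, but the negative B result almost vanishes in Gulbarga.

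**Step 5: equation (2) as printed.** Leaving covariates aside, it has 4 share terms, 3 group terms and 12 interactions: 19 columns. The four interactions for a group sum to that group's indicator, so each gamma_h is redundant and the rank is 16.

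Suppose there is no spillover. For group D only the beta terms apply. They must give the D mean at every share vector summing to 1, so each beta_h equals the D mean. Moving one share alone by 0.4 shifts a D household's prediction by 0.4 × D mean.

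For groups A, B and C the shift depends on which redundant term is dropped. As an illustration, take an A mean of 14 and a D mean of 10. An A household's prediction shifts by 0.4×10 = 4.0 if the D-share interactions are dropped, and by 0.4×14 = 5.6 if the gammas are dropped.

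**Step 6: proper share vectors.** Raising B by 0.4 at the expense of arm k changes a B household's prediction by 0.4 × [(beta_B - beta_k) + (lambda_BB - lambda_Bk)]. The answer depends on k even when the shares sum to 1.

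**The case against.** The strongest reply is that the plan leans towards D as reference. Section 7.1 takes D as the comparison group for the household effects and lists the shares for A, B and C, and equation (4) omits one share. If D always gives way, all three figures in the table are positive. This narrows the ambiguity but does not remove it. The plan never states this convention for the predictions, and it cannot serve a group D household, whose own share can rise only at the expense of A, B or C.

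A second reply is that an ITT effect compares arm h with D at the same shares, so the beta terms cancel. They do, but the interaction terms remain and still depend on the displaced arm. In the illustration above, moving the A share alone changes the A-versus-D effect by 0 or by 0.4×(14 - 10) = 1.6, according to the term dropped.

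A third reply is that section 7.1 maps each village arm to a full share vector, and that a share of 100% fixes the mix. Both are true. Predictions at a Table 1 row are well defined, but choosing which two rows to compare is still choosing the displaced arm. A share of 0% leaves the mix open.

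A reader might go further and infer that the plan's spillover analysis as a whole is undefined. It is not: the pooled A/B/C share, the total eligible share, the Wald test and the enrolment-rate model in equation (3) need no displaced arm.

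**Conclusion.** The point stands for the arm-specific own-share predictions in the four-share model. The plan does not define them, and equation (2) as printed can produce an apparent spillover from none. The plan should be amended here.

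On size, a 40-point rise in the C share changes implied enrolment by between +23.4 and -7.9 points, and the same rise in B by between +28.2 and -3.2. C is the stronger case. These figures assume equal take-up within an arm across village arms. The plan treats that as open, since section 7.1 applies its spillover test to take-up as well.

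Two stronger readings are not supported. A reader might infer that the reported spillover is shown to take either sign. The reversal is shown for enrolment only; it carries over to outcomes only if spillovers run through village enrolment, as equation (3) models. A reader might also infer that the false spillover is 0.4 times the outcome mean for everyone. That holds for group D with the D mean; for A, B and C no single figure exists, because the equation is not identified as printed.

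**What to change.** 1. Keep equation (2) but write it in an identified form, for example with an intercept and three shares, D omitted, in the main effects and the interactions.
2. Require every share-based prediction to use a full share vector that sums to 1 and to name the displaced arm, including predictions for group D households.
3. Report alongside, within each household group, the randomised one-for-one contrasts: III v IV (A for D), I v IV (A for B), II v IV (A for C), III v I (B for D), III v II (C for D) and I v II (B for C).
4. Keep village arm V in the model-based estimates. It holds 20% of villages and differs from every other arm in all four shares, so no one-for-one contrast uses it. Replacing the model with pairwise contrasts would lose arm V, and with it the power and extrapolation for which section 7.1 adopts equation (2).

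The cost is a change of SAP wording. Randomisation and data collection are untouched, and the contrasts are differences between means that the planned models already estimate.
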